16.8 Consultants. Vendors. Third Parties: N/A

16.9 Links to identifiable data: Each participant will be assigned a unique study ID that will consist of a series of numbers and letters that will have no meaning to any of the individual's personal identifying characteristics. The investigators will use this ID to track each individual participant in the research database. There will be no identifiers in this database. The identifiers will be maintained in separate, secure, encrypted, password-protected database in a different physical location. This separate database for the identifying information will also include the study ID so that the investigators can link research data to individuals when necessary. Electronic data bases, encrypted on University servers and password protected, only accessible to the investigators. Limited paper files may be maintained in locked filing cabinets in locked offices, but these will be minimized and will include consent form copies and a minimal amount of participant information if needed in hard copy. No research information will be placed in any sort of medical, employment, or educational record.

MEDICAL PROTOCOL (HRP-590)

PROTOCOL TITLE: Exercise and the Gut Microbiome R21

VERSION DATE: 05/11/2022

16.10 Sharing of Data with Research Team Members: We will share research data on a limited basis between research team members. However, when we do share data, we will do so via our University Box accounts.

16.11 Storage and Disposal of Paper Documents: Limited paper files may be maintained in locked filing cabinets in locked offices near the PI, but these materials will be minimized and will include consent form copies and a minimal amount of participant information if needed in hard copy. No research information will be placed in any sort of medical, employment, or educational record. Any paper materials will be kept for a minimum of 3 years after which the materials will be shredded and disposed of via proper means.

17.0 Confidentiality

17.1 Data Security: As reviewed previously, we have numerous safeguards in place to protect data integrity—all of which will be under the oversight of the PI. Our research team is qualified to conduct this oversight given past experience conducting randomized trials. First, all data will be double entered separately by two individuals which will allow us to check for data entry errors. Blood, stool, and salivary sample data will be examined for computational value errors associated with out-of-range variables. All data will be examined for outliers and improbable values. These procedures will ensure protection of the study's internal validity. Second, to protect the participants' health-related information, we will deidentify each participant's data. In detail, and as discussed in section 16.1, each participant will be assigned a unique study ID that will consist of a series of numbers and letters that will have no meaning to any of the individual's personal identifying characteristics. The investigators will use this ID to track each individual participant in the research database. There will be no identifiers in this database. The identifiers will be maintained in separate, secure, encrypted, password-protected database in a different physical location. This separate database for the identifying information will also include the study ID so that the investigators can link research data to individuals when necessary. Electronic data bases, encrypted on University servers and password protected, only accessible to the investigators. Limited paper files may be maintained in locked filing cabinets in locked offices, but these will be minimized and will include consent form copies and a minimal amount of participant information if needed in hard copy. No research information will be placed in any sort of medical, employment, or educational record.

18.0 Provisions to Monitor the Data to Ensure the Safety of Participants

MEDICAL PROTOCOL (HRP-590)

PROTOCOL TITLE: Exercise and the Gut Microbiome R21

VERSION DATE: 05/11/2022

This study involves no greater than minimal risk to participants.

18.1 Data Integrity Monitoring. Our research team is qualified to conduct this oversight given past experience conducting randomized trials. First, all data will be double entered separately by two individuals which will allow us to check for data entry errors. Blood, stool, and salivary sample data will be examined for computational value errors associated with out-of-range variables. All data will be examined for outliers and improbable values. These procedures will ensure protection of the study's internal validity. Second, to protect the participants' health-related information, we will deidentify each participant's data. In detail, and as discussed in section 16.1, each participant will be assigned a unique study ID that will consist of a series of numbers and letters that will have no meaning to any of the individual's personal identifying characteristics. The investigators will use this ID to track each individual participant in the research database. There will be no identifiers in this database. The identifiers will be maintained in separate, secure, encrypted, password-protected database in a different physical location. This separate database for the identifying information will also include the study ID so that the investigators can link research data to individuals when necessary. Electronic data bases, encrypted on University servers and password protected, only accessible to the investigators. Limited paper files may be maintained in locked filing cabinets in locked offices, but these will be minimized and will include consent form copies and a minimal amount of participant information if needed in hard copy. No research information will be placed in any sort of medical, employment, or educational record.

18.2 Data Safety Monitoring. N/A

19.0 Provisions to Protect the Privacy Interests of Participants

19.1 Protecting Privacy: We will have participants complete the demographic questionnaire in a private room well-ventilated within the Epidemiology Clinical Research Center. Further, we will conduct all measurements of weight, waist circumference, and blood pressure in this same well-ventilated room within this building as well. These data will not be spoken aloud. Finally, all blood collection will occur at the Epidemiology Clinical Research Center and performed by an experienced phlebotomist in the well-ventilated private room, with the salivary collection occurring within a private room in this facility too.

MEDICAL PROTOCOL (HRP-590)

PROTOCOL TITLE: Exercise and the Gut Microbiome R21

VERSION DATE: 05/11/2022

19.2 Access to Participants: We will only request access to each participant's home address, email, and phone numbers to ensure that we can contact participants to set up weekly walking sessions or determine a schedule of home-based walking sessions. We will otherwise not request access to medical records or any other source of private information about the participants.

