4.0 Study Intervention(s)/Investigational Agent(s)

4.1 **Description:** Following baseline data collection, participants will be randomized into one of two study groups using PROC PLAN (SAS 9.4) and a 1:1 allocation ratio.

GROUP 1 (aka, Experimental group): participants will complete 3 walking sessions/week for a total of 8 weeks (24 total sessions). Walking sessions will either take place on new commercial treadmills in the Epidemiology Clinical Research Center or remotely at or around a participant's home (see below). Regardless of the walking location, walking sessions will be 30 min in duration during intervention weeks 1 through 4 and a minimum of 45 min each during intervention weeks 5 through 8.

GROUP 2 (aka, Control group): participants will be asked to maintain their usual PA during the initial 8-week intervention period but will undergo all data collection procedures as outlined for the experimental group (See Section 5.2).

Experimental group participants who want to forego in-person exercise sessions on the University of Minnesota campus due to logistical constraints or the COVID-19 pandemic will modify the exercise intervention in the following manner:

MEDICAL PROTOCOL (HRP-590)

PROTOCOL TITLE: Exercise and the Gut Microbiome R21

VERSION DATE: 05/11/2022

Experimental group participants will engage in the same frequency and duration of walks as described above, but with a change in location to either: (a) in neighborhood or backyard walk (weather permitting, maintaining physical distancing); (b) on a treadmill within their home; and (c) in the hallway of their home if options a. and b. are not possible.

To monitor physical activity levels and ensure remote compliance: we will monitor to ensure that participants are completing their home-based walks at the proper duration and intensity using the Fitabase® platform. (See more information on the data security of Fitabase® in Section 16.7)

4.2 **Drug/Device Handling:** N/A

4.3 **Biosafety:** N/A

4.4 **Stem Cells:** N/A

5.0 **Procedures Involved**

5.1 **Study Design:** We will employ a 100-participant, 8-wk, randomized 2-arm parallel trial design with a 1:1 allocation ratio.

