5.2 **Study Procedures:** All eligible and consented participants will complete a 3-week run-in phase during which baseline outcome assessments will be performed. During run-in weeks 1 and 2, participants will wear a Fitbit Inspire 2 smartwatch and complete three unannounced dietary recalls. During the run-in week 3 (see table below), participants will consume their 3-day standardized meal plan on days three through five, obtain a fecal sample, and complete a study assessment visit. To quantify compliance with the 3-day meal plan, participants will be provided with a paper checklist of all foods to be consumed, and will be asked to indicate which foods were consumed and to document any deviation. The study assessment visit will include a fasting blood draw, blood pressure in triplicate, weight measure and body fat assessment in duplicate, and a saliva sample. Following successful completion of all measures, participants will then be randomized into one of the two study groups using PROC PLAN (SAS 9.4) and a 1:1 allocation ratio.

Group 1 (Experimental group): Participants will complete 3 treadmill walking sessions/week (24 total sessions) over 8 weeks at or around their home or in-person within the Epidemiology Clinical Research Center. Each walking sessions will be 30 min in duration during intervention weeks 1

MEDICAL PROTOCOL (HRP-590)

PROTOCOL TITLE: Exercise and the Gut Microbiome R21

VERSION DATE: 05/11/2022

through 4 and 45 min during intervention weeks 5 through 8. Notably, this exercise dose (i.e., intensity x session duration x weekly frequency x intervention length) is equivalent to, or greater than, that employed in most existing human studies of exercise and the gut microbiome in addition to the exercise dosage observed necessary to yield meaningful cardiometabolic changes.⁷² Therefore, while the dose is 'modest', it reflects what is relevant in real-world interventions and appropriate for overweight or obese sedentary individuals.

During week 4, participants will again consume their 3-day standardized meal plan, obtain a fecal sample, and complete a study assessment visit (same measures as described above for the 3-week run-in, except no fasting blood draw will be taken).

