6.0 Data and Specimen Banking

6.1 **Storage and Access:** We will initially collect data on paper after which we will transfer these data to computer spreadsheets for export to statistical packages, with this data entry conducted separately by two individuals to ensure data integrity. All PHI will be stored in a folder on the University of Minnesota's Box drive which is HIPAA compliant. All paper-based data will be stored in a locked file cabinet within the West Bank Office Building near the PI's office for a minimum of three years after the last participant has completed data collection. We will also store the de-identified electronic data for a minimum of three years on a server within the Division of Epidemiology and Community Health.

Buffy coat and serum from blood draws and saliva from salivary collection will be stored for up to 20 years in the PI's freezers located at the

MEDICAL PROTOCOL (HRP-590)

PROTOCOL TITLE: Exercise and the Gut Microbiome R21

VERSION DATE: 05/11/2022

Epidemiology Clinical Research Center or MoosT 1-355. All NIH procedures and University policies for the protection of confidentiality will be followed. Identifying data will be kept confidential, and only de-identified data will be shared.

6.2 **Data:** We will collect the following data: Serum, plasma, buffy coat, saliva, stool samples, Fitabase activity app data, food recall data, questionnaire data, and anthropometric data. The following data will be banked for future use if the participant consents: Serum, plasma, buffy coat, stool, and saliva. Otherwise, we will properly dispose of these specimens. All data will only be linked via a unique identification number. No identifying information will be included.

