12.0 Withdrawal of Participants

12.1 Withdrawal Circumstances: We do not foresee any circumstances under which participants will be withdrawn from the research without their consent. Participants who discontinue from the active intervention due to illness or injury will still be invited to complete all study measures at all data collection time points.

12.2 Withdrawal Procedures: For participants who ask to withdraw from the study voluntarily, no additional data will be collected and participants would be compensated at the prorated rate as described in Section 11.4. would still be compensated according to the table above. However, data from the participant's time in the study will still be used in data analysis when employing an intent-to-treat analysis approach.

12.3 Termination Procedures: We do not foresee any circumstances that would result in the termination of the study for any individual.

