13.0 Risks to Participants

13.1 Foreseeable Risks: The current study present no greater than minimal risk to participants. However, we will be taking precautions to ensure any potential risk from study participation is minimized. Per standard procedures during exercise intervention studies, we will ensure participants have no contraindications to exercise participation. However, we must note that any type of physical activity participation, even a walking exercise intervention like that of the current study, does carry risk in any population. Risks associated with exercise participation include

MEDICAL PROTOCOL (HRP-590)

PROTOCOL TITLE: Exercise and the Gut Microbiome R21

VERSION DATE: 05/11/2022

dizziness, nausea, muscle soreness, fatigue, fainting, joint pain, shortness of breath, muscular strains/sprains, and cramping. We will minimize these risks by allowing participants to complete a 5-10-minute warm-up of slow walking prior to each exercise session.

Some potential psychological stress or embarrassment may also be associated with filling out the study questionnaire and/or undergoing measurements of weight, waist circumference, and blood pressure in addition to the collection of stool samples and saliva. Risks will be minimized by collecting this data in a private setting, either at their home or at the ECRC, depending upon the measure in question.

As with all blood draws, there may be a modest amount of pain (equivalent to that of a pin prick) and lightheadedness associated with the collection of approximately 3 tablespoons of blood for each of three blood draws. We will minimize this risk by employing an experienced and trained phlebotomist for blood draws. Overall, the anticipated benefits to science outweigh the risks.

Finally, to prevent any threat of a COVID-19 infection, we will follow all UMN/OVPR/ECRC protocols while the participant is at the ECRC and encourage masking and physical distancing if any walks are done outside of the ECRC environment.

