20.0 Compensation for Research-Related Injury

20.1 Compensation for Research-Related Injury: This research does not involve greater than minimal risk to participants.

20.2 Contract Language: In the event that this research activity results in an injury, treatment will be available, including first aid, emergency treatment and follow-up care, as needed. Care for such injuries will be billed in the ordinary manner to you or your insurance company. If you think that you have suffered a research related injury, let the study know right away.

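### The protocol text sets out no systematic adverse-event collection: section 18.2 is N/A and harms reach the study only if participants volunteer them

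*Combined protocol and SAP*

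**What the plan says.** Section 18.2 consists of "18.2 Data Safety Monitoring. N/A". Section 18.0 opens by classing the study as minimal risk, and section 18.1 deals with double data entry, range checks and de-identification.

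Section 5.2 lists the content of the baseline visit: "fasting blood draw, blood pressure in triplicate, weight measure and body fat assessment in duplicate, and a saliva sample". Week 4 repeats this without the blood draw, and week 8 repeats it in full. The data types in section 6.2 include "stool samples, Fitabase activity app data, food recall data, questionnaire data, and anthropometric data".

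On harms, section 13.1 names nine linked to exercise, among them "dizziness, nausea, muscle soreness, fatigue, fainting, joint pain", and gives preventive steps. Section 4.1 places the walks "in the Epidemiology Clinical Research Center or remotely at or around" the participant's home, and says of remote walkers that "we will monitor to ensure that participants are completing their home-based walks at the proper duration and intensity".

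On stopping, section 12.1 says: "Participants who discontinue from the active intervention due to illness or injury will still be invited to complete all study measures". Under section 12.2, data collection ends when a participant withdraws voluntarily.

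On reporting, section 20.2 says: "If you think that you have suffered a research related injury, let the study know right away".

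**The concern.** A harm that nobody asks about cannot be recovered at analysis. Under section 20.2 the participant must notice the event, attribute it to the research and then volunteer it. A strain that does not stop someone walking could easily fail at one of those steps, particularly when the walk is done at home with no staff present.

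Reporting that depends on the participant also tends to follow contact with staff, and contact differs by arm. If the trial later describes harms by arm, more events among walkers could partly reflect more chances to mention them. What is at stake is participant safety and the ability to report harms fairly. The plan proposes no harm comparison, and the Shannon Index, SCFA and CMDrisk estimates do not depend on this point.

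**Working it through.** There is no stated figure to reproduce. The check is to read each place where an adverse-event procedure could sit and see what is there.

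1. **Monitoring (18.1, 18.2).** 18.1 protects data quality and confidentiality. 18.2 is N/A. Neither says how an event is elicited, recorded or acted on.
2. **Visits (5.2).** The week-4 and week-8 content is defined by reference to the baseline list, which contains measurements and samples only. The COVID-19 screening before visits applies to both arms and is an infection check, not a question about exercise harms.
3. **Safety procedures (13.1).** Section 5.2 sends the reader here for participant safety. The nine harms are dizziness, nausea, soreness, fatigue, fainting, joint pain, breathlessness, strains or sprains, and cramping. The text gives prevention (contraindication screening, a warm-up, a trained phlebotomist) and no recording step.
4. **Data and analysis (3.1, 3.2, 6.2, 15.1 to 15.3).** No outcome, named data type or analysis is an adverse-event variable. Questionnaire data are mentioned in 6.2 but their content is not specified.
5. **Stopping (12.1, 12.2).** 12.1 presupposes that the team will sometimes know that illness or injury ended the walking, and keeps those people in follow-up. No step records the reason. After voluntary withdrawal nothing more is collected.
6. **Home walks (4.1, 16.7).** Fitabase and the walk log would reveal a missed or shortened walk. No step is stated that records why it was missed.
7. **Reporting (20.2).** This is the only written route, and the participant must start it.

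**Contact by arm.** Both arms have the two assessment visits after randomisation, the dietary recalls in weeks 7 and 8, and the COVID-19 screening. Walkers may also have on-site sessions (4.1), contact to arrange weekly sessions or a home-walking schedule (19.2), monitoring of their walks (4.1) and a walk log (16.7). The compliance contacts in 16.5 are not limited to one arm, but compliance with walking concerns walkers only. The direction is therefore clear: walkers have more occasions to mention an event, even when they walk at home. The amount is not. The protocol does not give the share of sessions held on site, the number of scheduling or compliance contacts, or the chance that an event is mentioned at a contact. A total of contacts per arm would be incomplete, and a reporting imbalance cannot be calculated.

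**The case against.** The strongest reply is that silence in this document is weak evidence. Section 5.2 says the data collection forms are held on ETHOS, where they cannot be seen. Section 6.2 mentions questionnaire data, and section 13.1 still refers to a study questionnaire. The revision history records that a questionnaire at each assessment visit was removed, and current section 5.2 lists none, so the 13.1 wording may be a leftover; the text does not settle it. An adverse-event item could be on one of those forms. This stands, and it limits the point to what the protocol text describes.

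A second reply is that N/A follows from the minimal-risk classification. The intervention is walking for 30 to 45 minutes. A positive PAR-Q answer needs a doctor's note before enrolment, and first-aid equipment, a defibrillator and CPR-certified staff are provided. This supports having no monitoring board and keeps the severity low. It does not supply a means of recording events, and the equipment is on site only.

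A third reply is that section 12.1 and the walk monitoring would bring the more serious events to light. That is partly right for injuries that stop the walking. It does not reach events that leave walking unchanged, events in controls, or the reasons for withdrawal.

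A reader might infer that the trial will collect no adverse events, or that harm reporting is biased by a known amount. The documents support neither: the forms are unseen, and the inputs for an amount are not given.

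**Conclusion.** The point holds in a limited form. The protocol text describes no systematic adverse-event collection: the monitoring section is empty, the visits after randomisation contain no question, and reporting is left to the participant, although exercise harms are named and home walking is allowed. Unequal capture by arm is plausible because walkers have more contact with staff; its size is unknown.

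A reader might also infer that the trial's conclusions are at risk. They are not: no efficacy estimate changes. This is a minor and inexpensive safety improvement in a trial declared to be minimal risk. The conclusion assumes that the visits run as section 5.2 describes. If an ETHOS form already asks the question, what remains is to cite it, record reasons for stopping and report by arm.

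**What to change.** Replace the N/A in section 18.2 with three provisions.

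1. Ask one identically worded adverse-event question of both arms at the existing week-4 and week-8 visits. The investigator reviews the answers and decides whether walking continues and whether the event must be reported. The participant-initiated route in 20.2 stays for anything urgent.
2. Record the reason for any study withdrawal, in either arm, and for any discontinuation of walking. Amend section 12.2 so that a reason can be noted at the time of withdrawal if the participant offers it; otherwise the provision conflicts with the rule that collection stops.
3. Report by arm the events from the visit question (denominator: those asked) and the withdrawals due to illness or injury (denominator: all randomised). List session and walk-log events separately for the exercise arm, since controls have no counterpart.

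If an ETHOS form already holds the question, cite it in 18.2, state the investigator's review there, and add provisions 2 and 3.

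The cost is one form item, one reason field and a protocol amendment, with no new visits. The limits are real. Participants know their arm, so recall and attribution may differ even with identical wording, and a question asked every four weeks will miss minor events. Uncommon harms cannot be excluded with 50 randomised per arm, or 50 × 0.80 = 40 if the 20% attrition in section 10.1 applies after randomisation. With no events of a given kind in an arm, the one-sided 95% upper bound would be 1 − 0.05^(1/50) = 5.8% at 50, or 1 − 0.05^(1/40) = 7.2% at 40. These bounds describe what the fix could show; they do not measure the gap.
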